#### *Food Plan Feasibility (food plan satisfaction survey collection):*

- *Any negative outcomes, overall cost-prohibitiveness, support needed, and barriers encountered will be assessed with a food plan satisfaction survey at 5 and 9 weeks that will examine the feasibility of the food plan. Qualitative data will be thematically summarized for representative quotes.*

### Tertiary Outcome measures:

#### *Pain Visual Analog scale (VAS) collection:*

- We will collect subjective pain levels from participants over 9 weeks on a 10-point scale. A pain visual analog scale will give a numeric measurement of pain between “worst pain” and “no pain.”

#### *The Patient-Reported Outcomes Measurement Information System (PROMIS-29):*

- We will collect general perception of health status as well as quality of life scores over 9 weeks from participants. The PROMIS-29 is a survey that will give a numeric measurement of physical and mental health status on a scale of 0 to 10 that has been validated in adults with multiple chronic conditions.

### Exploratory measures:

#### *Pain Visual Analog scale (VAS), The Patient-Reported Outcomes Measurement Information System (PROMIS-29), and Dietary Adherence associations:*

#### **Protocol**

Study Title: Integrative Medicine for Hypermobility Spectrum Disorder (HSD) and Ehlers-Danlos (EDS) syndromes: A mixed-methods feasibility study (IMforHSDandEDS)

PI: [name]

IRB #: DH10320/PRAF

Approval Date: 03.03.21

Version: 3.0

- We will evaluate any associations between symptom severity, perceived pain, health-related quality of life, and dietary composition cross-sectionally and longitudinally over the course of the 9-week intervention.

*Patient Assessment of Chronic Illness Care+ scores (PACIC+) collection:*

- We will collect general perceptions and attitudes regarding the experiences of chronic illness care and living with chronic illness among patients with HSD and EDS at baseline and 9 weeks.
- The Patient Assessment of Chronic Illness Care (PACIC+) is a validated survey shown to have good reliability, internal consistency, and better psychometric characteristics than other surveys on patient satisfaction. It is designed to assess the experience and satisfaction within the chronic care model of healthcare, which often results in repeated appointments over a long time interval. It retrospectively assesses experiences of chronic illness care and living with chronic illness over the past 6 months.

*Health history and anthropometric measurements:*

- Biological information will be captured regarding the patients' previous medical health history, age, sex, and gender at the baseline screening. We will also document BMI, weight, height, and estimated energy requirement measurements at baseline. We will record patient self-reported weight at 5 and 9 weeks and track any changes that occur. Any abnormal BMI values will be monitored appropriately for safety, and any changes in these measures will be analyzed in accordance with the overall effectiveness of the diet.
- We will also document any other patient-reported symptoms that are experienced in addition to HSD or EDS throughout the 9 weeks and document any changes that occur.
- Any current pain medications or supplements that the participants are taking for pain will also be recorded.

*Beighton score: range of motion measurements*

- A set of measurements that assess joint hypermobility through a 9-point scale will be documented during the in-office screening. For every joint that can be extended past a specified angle, 1 point is added to the patient's Beighton score. A score of 4 or more indicates that generalized joint hypermobility is present.
- The Beighton score will be obtained during the baseline screening.

*NUNM Multi-system Adverse Event questionnaire:*

- A multi-system AE questionnaire will be administered at each visit. As HSD and EDS are associated with a considerable list of comorbidities, we will obtain a baseline measure of the AE questionnaire for each participant so that we have documented any pre-existing conditions. We will check on these conditions throughout the 9 weeks to ensure that symptoms have not worsened, in addition to noting any new occurrences. We will monitor these symptoms closely and recommend cessation of the food plan if a patient feels that any of their symptoms have been exacerbated.

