#### **Protocol**

Study Title: Integrative Medicine for Hypermobility Spectrum Disorder (HSD) and Ehlers-Danlos (EDS) syndromes: A mixed-methods feasibility study (IMforHSDandEDS)

PI: [name]

IRB #: DH10320/PRAF

Approval Date: 03.03.21

Version: 3.0

Ehlers-Danlos syndromes (EDS), in order to determine the recruitment potential in this population and to measure the ability of individuals to complete the program. Participants will be prescribed a food plan, and adherence to and feasibility of the food plan will be measured through participant food tracking and a subjective assessment of the food plan in a brief satisfaction survey. This study aims to recruit 20 patients with HSD or EDS and make preliminary observations regarding the effects of integrative medical care on pain reduction and improved quality of life. Participants will be given a 1-week lead-in to track their general diet prior to starting their prescribed food plan, and associations will be recorded between symptom severity and diet as an exploratory analysis. Patient assessment of chronic illness care and living with a chronic illness will also be captured; to assess the experiences of patients with HSD or EDS, as well as their perceptions of previous medical care and patient-centered medicine, and any changes in these attitudes over the course of 9 weeks. Available studies assessing treatments for HSD or EDS provide insufficient evidence for treatment options; this project studies a novel intervention focused on nutrition and self-management counseling, developed in conjunction with a qualified physician, and would allow us to gain valuable information regarding the feasibility of employing the intervention as well as preliminary data on its effect on health outcomes.

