## Protocol

Study Title: Integrative Medicine for Hypermobility Spectrum Disorder (HSD) and Ehlers-Danlos (EDS) syndromes: A mixed-methods feasibility study (IMforHSDandEDS)

PI: [name]

IRB #: DH10320/PRAF

Approval Date: 03.03.21

Version: 3.0

**B.3 Tertiary Aim:** To examine the effect of a 9-week integrative medicine intervention on overall perceived pain and quality of life in patients with Hypermobility Spectrum Disorder (HSD) or Ehlers-Danlos syndromes (EDS).

- Outcome Measures 3: Participants will complete a Visual Analog Scale for Pain (VAS Pain) and a 29-Item profile HRQoL Survey (PROMIS-29) at baseline, 5, and 9 weeks.

In order to better understand the needs of the patient population, we will also address the following exploratory aims, as far as we are able. These aims can be considered to be independent of the effects of treatment.

**B.4 Exploratory Aim 1:** To evaluate any associations between symptom severity, perceived pain, quality of life, and diet among patients with Hypermobility Spectrum Disorder (HSD) or Ehlers-Danlos syndromes (EDS).

- Participants will be given a 1-week lead-in to establish baseline food patterns before starting the prescribed food plan. Associations of dietary composition, patient-reported symptoms, as well as overall perceived pain and quality of life scores will be examined, both cross-sectionally at intake and longitudinally over the 9 weeks of the intervention.

**B.5 Exploratory Aim 2:** To assess the experiences of chronic illness care and living with chronic illness among patients with Hypermobility Spectrum Disorder (HSD) or Ehlers-Danlos syndromes (EDS).

- Outcome Measure 5: Participants will complete a 26-item survey, Patient Assessment of Chronic Illness Care (PACIC+), that evaluates areas of patient self-management within the chronic care model of healthcare. The PACIC+ ascertains attitudes regarding patient-centered care, living with chronic illness, and chronic illness care; it will be completed by participants at baseline and 9 weeks.

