### **E.4 Participant and Procedure Schedule**

#### **E.4.1 Overview**

The study is comprised of 1 in-person screening, 2 follow-up visits, and 2 telephone or email check-in correspondences for additional support. The in-person screening and 2 virtual follow-up visits will take place at the Healthy Living Community clinic. Virtual follow-up study visits will take place via the Zoom video platform utilized by ChARM TeleHealth, a web-based and HIPAA compliant server maintained by the Healthy Living Community clinic and will occur at 5- and 9-weeks post-enrollment.

During the in-office screening, participants will have their joint mobility measured in accordance with the Brighton Scoring System to confirm that they meet the diagnostic criteria for Hypermobility Spectrum Disorder. Participants who are diagnosed using the Brighton criteria and meet other eligibility criteria will then be asked to provide informed consent (E.4.3) and enrolled in the study if willing. The Clinical Investigator will capture a complete and detailed medical history of enrolled participants, discuss family and social support, as well as prescribe a food plan. The CI will also assess the patient's current self-management strategies and provide general behavioral and psychosocial support. During the 2 follow-up visits, the Clinical Investigator will revisit these self-management strategies. As scheduling visits may be difficult at precisely 5 and 9 weeks, we will leave some flexibility for these points in time to accommodate the schedules of the Clinical investigator, the student researcher, and the participants.

At 2 and 6 weeks, the participants will be contacted by the student researcher to answer any questions, provide nutritional and psychosocial support, monitor for any adverse events, and offer solutions to any dietary challenges. Participants will also be assessed at all study visits for any adverse events.

Participants will be asked to complete pain (VAS), and health-related quality of life (PROMIS-29) instruments at baseline, 5, and 9 weeks. Adherence to the dietary recommendations, as well as the feasibility of food tracking will be obtained using *MyFitnessPal*, a food tracker app throughout the 9 weeks. A food plan satisfaction survey will be collected at 5 and 9 weeks. Participants will fill out the

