#### **Protocol**

Study Title: Integrative Medicine for Hypermobility Spectrum Disorder (HSD) and Ehlers-Danlos (EDS) syndromes: A mixed-methods feasibility study (IMforHSDandEDS)

PI: [name]

IRB #: DH10320/PRAF

Approval Date: 03.03.21

Version: 3.0

patient assessment of care for chronic conditions (PACIC+) at baseline and the close-out visit during week 9.

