#### **E.4.8 Visit # 3: Follow-up (9 weeks)**

During the final virtual visit, the student researcher will collect VAS pain measurements, patient assessment of care for chronic conditions (PACIC+), PROMIS-29 health-related quality of life scores and will assess participants for any adverse events using the NUNM standardized multi-system questionnaire.

The Clinical Investigator will discuss the social and familial support of the patient, provide psychosocial support, and address any concerns with the anti-inflammatory food plan. The CI will also assess the patient's current self-management strategies and provide suggestions for any adjustments to general behavioral and psychosocial support recommendations. Any current medications or supplements being used for pain that the participant is taking will also be documented, but no changes in medications will be required by the study. Current self-reported weight will also be documented.

At the final visit, patients will be encouraged to continue to eat a healthy diet but will be reminded that the study is complete and that they may alter their diet in whatever way they wish.

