#### Providing psychosocial support

Psychosocial support will be provided by both the Clinical Investigator, the student researcher, and *MyFitnessPal* throughout the 9-week program. Participants will receive behavioral, lifestyle, and dietary counseling all through a total of 3 office visits with the medical doctor, and 2 phone calls or e-mail check-in correspondences with the student researcher.

The student researcher has personal experience with both hEDS and Postural Tachycardia Syndrome (POTS), and similar to another EDS study, this will be disclosed to participants at the beginning of the interview in an effort to mitigate the power imbalance that often accompanies research. This may also help “instill greater confidence in participants” to share their experiences with a researcher and EDS individual who is also in their “in-group.” It will also be “emphasized that it [is] their stories that matter” for the purpose of the study.

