We will summarize Patient Assessment of Chronic Illness Care (PACIC+) scores in the sample, at both baseline and study end, and mean (SD). We will also test whether the scoring changed after participating in integrative medicine intervention, using a paired t-test.

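### Does the 6-month recall of PACIC+ make its repeat at week 9 unfit for the planned before-after comparison?

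*Combined protocol and SAP*

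**What the plan says.** E.6 Measures, under the exploratory measures, describes the recall period of PACIC+: "It retrospectively assesses experiences of chronic illness care and living with chronic illness over the past 6 months". B.5 (Exploratory Aim 2) sets the timing: "it will be completed by participants at baseline and 9 weeks". E.4.1 repeats it, "patient assessment of care for chronic conditions (PACIC+) at baseline and the close-out visit during week 9", and E.4.8 lists the questionnaire among the week-9 data. The follow-up dates are not rigid, since E.4.1 adds that "we will leave some flexibility for these points in time" and gives no window.

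For analysis, E.9 (Exploratory Aim 2) summarizes scores at both times as mean and SD, then says: "We will also test whether the scoring changed after participating in integrative medicine intervention, using a paired t-test".

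Two statements of purpose matter. The abstract says the questionnaire addresses "perceptions of previous medical care and patient-centered medicine, and any changes in these attitudes over the course of 9 weeks". Section B introduces both exploratory aims as separable from any treatment effect and meant to clarify what this patient population needs. Nothing in the text available for review shortens the recall at week 9 or mentions the overlap. The PACIC+ form itself is not in that text.

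**The concern.** A before-after comparison is cleanest when the second measurement covers only time after the first. Here most of the week-9 recall period had already been rated at baseline. People already under the study clinic's care are excluded, so those shared weeks reflect care received elsewhere. If study care is experienced as better, a six-month answer at week 9 blends it with the earlier care, and the mean difference could be pulled toward zero.

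With up to 20 pairs, a null t-test could then be read as saying that experience of care did not change. As an illustration, suppose the in-study shift were 0.8 SD of the change score, all recalled weeks counted equally, and earlier care was steady. The visible shift would be 0.8 × 9/26 = 0.28 SD, and the power of a two-sided 5% paired t-test with 20 pairs would fall from 92% to 22%. All three conditions are assumptions.

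**Working it through.** The plan states no overlap figure and no sample size or power for PACIC+, so there is nothing of its own to reproduce.

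**Overlap of the windows.** Inputs: recall of 6 months, taken as 26 weeks (E.6); interval between administrations of 9 weeks (B.5, E.4.1).

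- Shared time: 26 − 9 = 17 weeks; 17/26 = 65%.
- New time: 9/26 = 35%.
- Taking 6 months as 24 weeks: 15/24 = 62.5%. Taking it as 365.25/14 = 26.09 weeks: 17.09/26.09 = 65.5%.
- Visit at 8 to 11 weeks (assumed, because no window is given): 18/26 = 69% to 15/26 = 58%.

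Most of the second window predates enrollment on every variant.

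**What the overlap does to the mean difference.** Let E be the mean level of experience in the earliest 9 weeks of the baseline window, M the level in the following 17 weeks up to enrollment, and S the level during the study. If every recalled week counts equally (assumed):

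- baseline score = (9E + 17M)/26
- week-9 score = (17M + 9S)/26
- difference = (9/26)(S − E)

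The shared 17 weeks cancel. The change at enrollment that one would like to see is S − M. Three cases, with assumed levels:

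| E | M | S | S − M | Paired difference |
|---|---|---|---|---|
| 2 | 2 | 3 | +1 | 9/26 = +0.35 |
| 2 | 3 | 3 | 0 | 9/26 = +0.35 |
| 3 | 2 | 3 | +1 | 0 |

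The first row is the dilution one fears, and it needs steady experience before enrollment (E = M). In the second row the difference shows a gain although nothing changed at enrollment. So the overlap alone does not fix the direction of the error.

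**How far the size depends on recall weights.** Keep E = M and let an in-study week count r times an earlier week. The share of the in-study shift that appears in the difference is 9r/(9r + 17):

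- r = 1: 9/26 = 35%
- r = 2: 18/35 = 51%
- r = 3: 27/44 = 61%

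The documents give no value for r. They also do not say how much care participants had in the shared 17 weeks. Someone who had little would have little to blend in, so calendar weeks are only a rough stand-in for what the questionnaire rates.

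**How much study care lies between the two administrations.** E.5 promises "a total of 3 office visits with the medical doctor, and 2 phone calls or e-mail check-in correspondences with the student researcher". The first physician visit is the baseline PACIC+ visit and the third is the week-9 PACIC+ visit. E.4.4 describes the surveys after the consultation and E.4.8 describes them before it, though neither fixes the order. Only the second visit and the two check-ins certainly fall between, so the count of contacts does not settle r.

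**The case for a change.** The strongest case for acting is that E.9 does test change after the intervention, whatever Section B says about the exploratory aims. The 17 weeks are plain arithmetic, steady care before enrollment is a plausible default, and one caveat sentence with a confidence interval would cost almost nothing. The interval would be wide: its 95% half-width, t(0.975, n − 1)/√n, is 0.47 SD of the change score with 20 pairs and 0.55 SD with 15 (75% retention). A null result could therefore be over-read, and the conclusion section hopes to inform a larger study.

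Part of this stands. The overlap exists, it bears on a planned comparison, and a null PACIC+ result would be weak evidence that experience of care stayed the same. The rest does not lead to a change. A confidence interval addresses precision, not overlap. A caveat naming only a bias toward no change would be one-sided: there is no control group, and the student researcher who collects PACIC+ also gives support and discloses shared illness to build confidence, which could push scores upward. The overlap is also visible to any reader, because E.6 states the recall period and the two time points together.

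The one substantive alternative is to ask at week 9 only about care since the first study visit. That departs from the six-month recall described for this validated instrument and sets a 9-week window against a 26-week one. It exchanges one interpretive difficulty for another.

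**Conclusion.** No change is needed. About 17 of 26 weeks (65%; 58% to 69% for an assumed visit at 8 to 11 weeks) of the week-9 recall period was already covered at baseline, so the paired t-test shows whether scores moved without cleanly isolating experience of care during the study. The documents settle neither the direction nor the size of any distortion. The 35% figure holds only with equal weighting of weeks and steady care before enrollment.

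Keeping the instrument's described recall is a fair trade-off. If participants rate the same earlier care differently at week 9, that is itself a change in attitude toward previous care, which the abstract sets out to capture, and the baseline description of earlier care is untouched. Recruitment, retention, adherence, pain and quality-of-life results do not depend on PACIC+, and no decision rule uses it. An analyst can interpret the exploratory change with the stated recall period in view. This rests on the description in E.6, since the form and its week-9 instructions were not available.

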### **E.3.1 Inclusion Criteria**

- Age 18-65
- Beighton score of 4 or more to confirm joint hypermobility diagnosis
- Baseline VAS Score of 1 or more
- Not currently, or already a patient of [name] and Healthy Living Community
- Ability to provide written informed consent
- Willingness to participate in 9-week integrative medicine intervention (and make dietary and lifestyle changes)
- Willingness to attend 1 in-person screening visit and 2 virtual office visits (or 3 virtual visits, if medical documentation of Beighton score can be provided in advance of enrollment, and all other criteria are met).
- Access to an electronic device for *MyFitnessPal* food-tracker use (i.e mobile device, tablet, laptop)

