#### **E.4.4 Visit # 1: Screening (baseline)**

During the in-person screening visit, CDC Coronavirus Disease 2019 (COVID-19) doctor visit regulations will be followed, and all participants, the student researcher, and the Clinical Investigator will be required to wear facial masks, maintain a physical distance at 6 feet apart, and wash hands after all contact.

Participants will review the informed consent form with the student researcher, who will answer any questions. A signed form will be collected prior to initiating study-related activities. The Clinical Investigator (CI) will take range of motion measurements that will be obtained in accordance with The Beighton Scoring System to confirm that the participant meets the diagnostic criteria for Hypermobility Spectrum Disorder. BMI, height, and weight will also be collected. Participants will be screened for a history of disordered eating or eating disorders; if present; the participant will be referred to a specialized physician for treatment and excluded from the study. Participants with a body mass index (BMI) considered to be underweight, or less than 18.5, will also be excluded from the study. The CI will

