### **Protocol**

Study Title: Integrative Medicine for Hypermobility Spectrum Disorder (HSD) and Ehlers-Danlos (EDS) syndromes: A mixed-methods feasibility study (IMforHSDandEDS)

PI: [name]

IRB #: DH10320/PRAF

Approval Date: 03.03.21

Version: 3.0

their daily food tracking with the student researcher, and the data will be collected at 5 and 9 weeks. Participants will be given a 1-week lead-in period so that they can adjust to tracking their dietary intake before starting the food plan and will be instructed to contact the student researcher with any questions.

In the event that the baseline visit is conducted virtually, all procedures will be the same, except that the participant will provide medical documentation of a Beighton score of 4 or more, in lieu of a Beighton measurement being obtained at the visit. We will require informed consent prior to capturing this documentation. The participant will be asked to report their own height and weight. All other data will be captured electronically. Any participant who completes the baseline visit remotely will be invited to complete the Week 5 visit in person, if possible; if the Week 5 visit is completed in person, then weight, height, and Beighton score will be confirmed at that visit.

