#### **Protocol**

Study Title: Integrative Medicine for Hypermobility Spectrum Disorder (HSD) and Ehlers-Danlos (EDS) syndromes: A mixed-methods feasibility study (IMforHSDandEDS)

PI: [name]

IRB #: DH10320/PRAF

Approval Date: 03.03.21

Version: 3.0

used for pain that the participant is taking will also be documented, but no changes in medications will be required by the study. Current self-reported weight will also be documented.

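### Weight change mixes clinic and self-reported weights by participant and visit, with no rule for which pair of weights defines the change

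*Combined protocol and SAP*

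**What the plan says.** **Baseline, in person.** Section E.4.4 (Visit 1) states: "BMI, height, and weight will also be collected". It does not say outright that staff weigh the participant. That is inferred from the contrast with the virtual route below.

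**Baseline, virtual.** The inclusion criteria in E.3.1 permit this route: "or 3 virtual visits, if medical documentation of Beighton score can be provided in advance of enrollment". For these participants E.4.4 says: "The participant will be asked to report their own height and weight". They are invited to attend week 5 in person, and "if the Week 5 visit is completed in person, then weight, height, and Beighton score will be confirmed at that visit".

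**Follow-up.** The sections on Visit 2 (E.4.6) and Visit 3 (E.4.8) use the same sentence: "Current self-reported weight will also be documented". Section E.6, under health history and anthropometric measurements, repeats this: "We will record patient self-reported weight at 5 and 9 weeks and track any changes that occur".

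**Use.** E.6 gives the data two purposes. On safety: "Any abnormal BMI values will be monitored appropriately for safety". On benefit: "any changes in these measures will be analyzed in accordance with the overall effectiveness of the diet". Section E.9 plans a mean and SD for anthropometrics. It names no test of weight change, no rule for choosing between weights and no adjustment for how a weight was obtained.

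**The concern.** A clinic weight and a weight reported from home can differ when the body has not changed, because of the scale, clothing, time of day or the reporting itself. If one is the baseline and the other the follow-up, the difference between sources is added to the change. This is a single-group study, so no comparison arm carries the same shift and cancels it. A mean loss or gain could then be read as an effect of the diet when part or all of it comes from the switch of source.

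The mix also varies. Some participants switch source after baseline, some never switch, and some may switch at week 5 and back at week 9. A pooled mean therefore depends partly on how many people took each route, which the plan neither fixes nor says it will report.

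**Working it through.** The plan gives no sample size, SD or expected value for weight change, so there is no figure of its own to reproduce. The check traces the source of each weight and then carries an assumed gap through to the mean.

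**Inputs from the documents.** Weight source by route and visit (E.3.1, E.4.4, E.4.6, E.4.8, E.6); mean and SD as the planned summary (E.9); 20 participants and a 75% retention goal (B.1), so 0.75 × 20 = 15 retained.

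**Assumed inputs.** The gap b, self-report minus clinic weight, is constant at −0.5 or −1.0 kg. The share f with an in-person baseline is 100%, 75%, 50% or 0%. The share g of virtual-baseline participants seen in person at week 5 is 0 or 1. The sign of b is also assumed; a positive b reverses every sign below.

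**Step 1: contribution of b to one participant's change.** Write a clinic weight as W and a self-reported weight as W + b.

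| Route | Baseline | Week 5 | Week 9 | Error in week 5 change | Error in week 9 change |
|---|---|---|---|---|---|
| In-person baseline | clinic | self-report | self-report | b | b |
| Virtual baseline, virtual week 5 | self-report | self-report | self-report | 0 | 0 |
| Virtual baseline, in-person week 5 | self-report | clinic | self-report | −b | 0 |

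The third row assumes that the clinic weight is used at week 5 and that the self-reported baseline is kept. The plan states neither.

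**Step 2: shift in the mean.**

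- Week 9: f·b
- Week 5: f·b − (1 − f)·g·b

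| f | Week 9, b = −0.5 | Week 9, b = −1.0 | Week 5, b = −1.0, g = 0 | Week 5, b = −1.0, g = 1 |
|---|---|---|---|---|
| 100% | −0.50 kg | −1.00 kg | −1.00 kg | −1.00 kg |
| 75% | −0.375 kg | −0.75 kg | −0.75 kg | −0.50 kg |
| 50% | −0.25 kg | −0.50 kg | −0.50 kg | 0 kg |
| 0% | 0 kg | 0 kg | 0 kg | +1.00 kg |

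For example, at f = 50% and g = 1, the week 5 shift is 0.5 × (−1) − 0.5 × 1 × (−1) = 0. Week 5 and week 9 can therefore carry different shifts in the same participants. None of these shifts shrinks with a larger sample.

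**Step 3: BMI.** The shift is |b|/height². At an assumed 1.65 m, 0.5/2.7225 = 0.18 and 1.0/2.7225 = 0.37 kg/m².

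**Step 4: change within one source.** With self-report at both ends, (W₉ + b) − (W₀ + b) = W₉ − W₀. A constant b contributes 0 kg. A b that drifts between visits does not cancel.

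**Step 5: illustration only.** If weight change were tested with a two-sided 5% paired t-test, which the plan does not propose, with all baselines in person and no true change, the noncentral t with noncentrality |b|/(SD/√n) gives these rejection rates:

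| Assumed SD of change | n | Gap 0.5 kg | Gap 1.0 kg |
|---|---|---|---|
| 2 kg | 15 | 14.7% | 43.8% |
| 2 kg | 20 | 18.6% | 56.5% |
| 3 kg | 15 | 9.2% | 22.5% |
| 3 kg | 20 | 10.9% | 29.4% |

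**The case against.** The strongest reply is about priority. Weight appears in none of the stated aims and is listed under exploratory measures. The study's conclusions rest on recruitment, retention and adherence, which do not use it. Follow-up is virtual, so self-report is the practical choice. All of this stands, and it limits how much the point matters. It does not remove the point, because E.6 still says the changes will be analysed in relation to the diet.

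Three stronger readings are tempting, and the documents do not support them.

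- A reader might infer that every change score is affected. The virtual-baseline route is self-report to self-report, so a constant gap cancels there, except at a week 5 visit held in person if the clinic weight is used.
- A reader might infer an inflated false-positive rate. E.9 names no test of weight change; its paired tests are for pain, quality of life and PACIC+. The rates in step 5 also rest on an assumed gap, an assumed SD and all baselines being in person. At an SD of 3 kg they are roughly half to two-thirds of those at 2 kg.
- A reader might infer that the underweight safeguard is compromised. The BMI exclusion is applied at baseline and uses no change score. E.6 speaks of monitoring abnormal values and sets no trigger based on change. Follow-up BMI would rest mainly on self-report with or without the change proposed here, so safety is not a good argument for it.

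**Conclusion.** The point holds as a gap in an exploratory measure. For participants with an in-person baseline, weight change compares a clinic weight with self-reports. For the others the source is the same throughout or switches only at week 5. No rule covers the difference.

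For an assumed constant gap of 0.5 to 1.0 kg, mean week 9 change moves by 0.5 to 1.0 kg if all baselines are in person, and by 0.25 to 0.5 kg if half are. The size and sign of the gap and the share on each route are assumptions. That the in-person weight is measured by staff is an inference, though the natural one. The primary feasibility results and the baseline BMI exclusion are unaffected. This is a cheap improvement, not a threat to the study's conclusions.

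**What to change.** - At an in-person Visit 1, ask for the participant's self-reported home weight before weighing, so that the clinic reading does not anchor the answer.
- Record the source of every weight, clinic or self-report, at every visit.
- State in E.6 and E.9 that weight change is computed from self-report to self-report only.
- At a week 5 visit held in person, record the self-report as well, and do not substitute the clinic weight in the change score.
- Keep clinic weights for the eligibility check and for describing the sample.

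The cost is one extra question, a source field and a sentence or two of text. The question has to be in place before in-person baselines are taken, since a home weight not asked for then cannot be recovered reliably. Self-reported change will remain noisy, and the fix does not remove a reporting difference that drifts over the nine weeks.
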